9.3.2 Analysis of Safety

No statistical analysis of safety data will be performed in this study. Safety will be assessed using the SAS with subjects included in the treatment group they actually received, regardless of their randomized treatment. The assessment of safety will include adverse events, clinical laboratory assessments, ECGs, physical examinations, and vital signs. Observed case data will be used.

Adverse events (AEs) will be coded using the most recent version of the Medical Dictionary for Regulatory Activities (MedDRA). The summarization of AEs will include only treatment-emergent AEs (TEAEs), defined as AEs that begin or worsen after randomization and ingestion of the first dose of study drug. TEAEs and SAEs will be summarized by system organ class (SOC), severity, and relationship to study drug for each treatment group. Deaths, withdrawal from study treatment due to AEs, and withdrawal from the study due to AEs will each be summarized by treatment group.

Safety laboratory data will be summarized by treatment group at baseline and at each post-baseline time point. Change from baseline to each time point, if appropriate, will also be summarized by treatment group. Baseline for safety laboratory data will be defined as the last pre-dose measurement (pre-dose Study Day 1/Visit T1 or prior). Frequency counts of new or worsening abnormalities will also be provided.

Vital signs data (value and change from baseline, where appropriate) will be summarized by treatment group at baseline and at each post-baseline time point. Baseline for vital signs data will be defined as the last pre-dose measurement (pre-dose Study Day 1/Visit T1 or prior). Abnormalities in ECGs and in PEs will be summarized.

All safety data will be listed.

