The following laboratory parameters will be summarized at baseline and at each post-baseline time point by treatment group. Additionally, CFBL to each time point (including end of treatment), if appropriate, for each of the following laboratory parameters will also be summarized by treatment group. If, for a given subject at a given visit, the absolute count of neutrophils are not provided but segmented and band neutrophils are, segmented and band neutrophils are summed to determine the absolute count of neutrophils. If only segmented neutrophils are provided, they are used as the absolute count of neutrophils. Similarly, if neutrophils/leukocytes are not provided at a given visit but neutrophils (segmented)/leukocytes are, neutrophils (segmented)/leukocytes are used as neutrophils/leukocytes. If a laboratory value is lower or higher than the detection limit, the value will not contribute to summary statistics but will be included in the listings.

- **Chemistry:** ALT, albumin, ALP, AST, bicarbonate, BUN, calcium, chloride, creatine kinase (CK), creatinine, gamma-glutamyl transferase (GGT), glucose, lactate dehydrogenase (LDH), phosphorus, potassium, sodium, (total) bilirubin, (total) protein, estimated glomerular filtration rate (GFR)
- **Coagulation:** prothrombin time, activated partial thromboplastin time, international normalized ratio
- **Hematology:** hemoglobin, hematocrit, leukocytes, basophils, eosinophils, lymphocytes, monocytes, neutrophils, platelets, red blood cell count, mean corpuscular hemoglobin concentration, mean corpuscular hemoglobin, mean corpuscular volume
- **Urinalysis:** pH, specific gravity, NGAL, creatinine, protein, protein/creatinine ratio, albumin, albumin/creatinine ratio

Out-of-range values will be assessed using shift tables. Laboratory values will be identified as low, normal, or high based on the normal ranges provided by the central laboratory. Shift tables for each parameter will display, for each treatment group, the number of subjects with low, normal, and high values at baseline and end of treatment. Additionally, a summary will be provided of the number of subjects who shifted to high or low during the study. The denominators will be the number of subjects at risk for shifting, ie, the subjects at risk for shifting to low are those with high or normal values at baseline, and the subjects at risk for shifting to high are those with low or normal values at baseline.

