Potentially clinically significant (PCS) tables will also be used to summarize out-of-range values for safety laboratory parameters. The PCS values are found in Table 3. The number and percent of subjects meeting the criteria below for single occurrences and consecutive (multiple) occurrences will be summarized by treatment group. The number and percent of subjects meeting the criteria below for single occurrences will be repeated for each statin-intensity stratum. Summaries will be given for any time post-baseline. The denominator for a given percentage will be the number of subjects who had a post-baseline assessment for the corresponding parameter. Additionally, for subjects with at least 1 post-baseline laboratory value meeting the PCS criteria, all laboratory values will be provided in a listing.

Table 3. Lab PCS Criteria

Laboratory Parameter	Unit	PCS Criteria
ALT	U/L	> 2 × ULN
AST	U/L	> 2 × ULN
BUN	mg/dL	> 2 × ULN
Creatine kinase	U/L	> 3 × ULN
Creatinine	mg/dL	> 0.3 increase from baseline
Estimated GFR	mL/min	Decrease > 15 from baseline
Hemoglobin	g/dL	Decrease > 1.5 from baseline
Urinalysis Parameter	Unit	PCS Criteria
Blood	-	present
Protein (qualitative)	-	present
Protein (quantitative)	-	> ULN
Protein/creatinine ratio	mg/mmol	> ULN

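### The protocol promises counts of new or worsening laboratory abnormalities, but for 28 of 35 blood parameters the SAP's laboratory tables count only the new ones

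*SAP*

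**What the plan says.** Protocol 9.3.2 (Analysis of Safety), and the synopsis in the same words, make a commitment for the safety laboratory data: "Frequency counts of new or worsening abnormalities will also be provided". Neither place defines worsening.

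SAP 12.2 (Clinical Laboratory Assessments) plans four by-arm laboratory outputs:

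- Descriptive summaries of values and of change from baseline. Change "for each of the following laboratory parameters will also be summarized by treatment group".
- A shift table that displays "the number of subjects with low, normal, and high values at baseline and end of treatment", with no grading inside the low or high category.
- A count of subjects who moved to high or to low during the study. Its denominators depend on baseline status alone. In one direction, "the subjects at risk for shifting to high are those with low or normal values at baseline". The rule for low values mirrors this and leaves out anyone who starts low.
- PCS counts at any time after baseline, using the criteria in Table 3. Here, unlike in the shift count, "The denominator for a given percentage will be the number of subjects who had a post-baseline assessment" of that parameter.

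SAP Section 8 lists the changes from the protocol's planned analyses. Dropping the worsening part of the laboratory count is not among them.

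**The concern.** The at-risk rule is a sound way to count new abnormalities, but it cannot count worsening. Anyone already high is outside the shift-to-high count however far the value then rises.

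Abnormal baselines are to be expected. Protocol 4.2 excludes ALP only above 2 × ULN and total bilirubin only above 1.5 × ULN, and subjects with Gilbert's syndrome may enter above that. It sets no specific limit for GGT, LDH, INR or aPTT.

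Some of the parameters concerned are ones the documents single out. SAP 6.3 names bilirubin, ALP and electrolytes for particular attention. Protocol Appendix E uses bilirubin, INR and eosinophilia in its hepatic criteria. What is at stake is a by-arm safety output that the protocol promises and a reader of the study report would look for. Efficacy is not affected.

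**Working it through.** The plan gives no figure on this point, so the check has three parts: count the parameters, compare the outputs, and follow one subject through them. No alpha or power figure depends on it.

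**1. Parameters without a PCS row** (lists in SAP 12.2; rows in SAP Table 3)

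- Blood parameters summarized: 19 chemistry + 3 coagulation ("prothrombin time, activated partial thromboplastin time, international normalized ratio") + 13 hematology = 35.
- Blood parameters with a Table 3 row: ALT, AST, BUN, CK, creatinine, estimated GFR, hemoglobin = 7.
- Without a row: 35 − 7 = 28. These are 13 chemistry (albumin, ALP, bicarbonate, calcium, chloride, GGT, glucose, LDH, phosphorus, potassium, sodium, total bilirubin, total protein), all 3 coagulation, and 12 hematology (all except hemoglobin). 13 + 3 + 12 = 28.
- Of the 7 rows, only creatinine, estimated GFR and hemoglobin are defined by change from baseline. ALT, AST, BUN and CK use a fixed ULN multiple. Parameters with no baseline-relative count: 35 − 3 = 32.

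**2. What each by-arm laboratory output counts**

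| Output | New abnormality | Worsening from an abnormal baseline |
|---|---|---|
| Values and change from baseline | not a count | not a count; enters mean, SD, median, minimum and maximum (SAP 9.2) |
| Low/normal/high table, baseline to end of treatment | yes, if present at end of treatment | no; stays in high/high or low/low |
| Shifted to high or low during the study | yes | no; excluded by the at-risk rule |
| PCS criteria | 7 blood parameters | 3 by change from baseline; 4 only when a ULN multiple is exceeded |

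For the 28 parameters, no entry in the last column is a count of worsening.

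**3. One subject** (illustrative values; the baseline is allowed by Protocol 4.2)

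ALP is 1.5 × ULN at baseline and 4 × ULN at end of treatment. The subject is not at risk for a shift to high, sits in the high/high cell, and has no PCS row. The rise enters the arm's change-from-baseline statistics and the listings. It also enters the adverse event tables if reported as an event.

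A parameter with a row can also be missed: ALT going from 1.1 to 1.9 × ULN stays under the 2 × ULN criterion.

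**4. Denominator of the shift count** (minor)

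The at-risk set does not require a post-baseline value. With 52 subjects per arm (SAP 9.1), and assuming for illustration that all are at risk, 2 have no post-baseline value and 5 shift: 5/52 = 9.6% against 5/50 = 10.0%.

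**The case against.** A reader might infer that worsening from an abnormal baseline is counted in no by-arm table, or is visible only as a diluted shift in means. The documents do not support either statement.

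- Protocol 8.1 has clinically significant abnormal values present at first dose reported as adverse events if they worsen. SAP 12.1 tabulates treatment-emergent events by arm and by stratum.
- SAP 9.2 includes minimum and maximum among the standard statistics, so the largest change in each arm is shown.
- All safety data are listed.

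These outputs limit the gap but do not supply the promised count. The adverse event route depends on the investigator's judgement. Protocol 8.1 does not require a result unconfirmed by repeat testing to be reported, and the tables are organized by preferred term rather than by laboratory parameter. A maximum shows one subject, not how many. Listings give no frequencies.

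Other points have some weight:

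- The 28 parameters overlap (PT with INR; hematocrit and red cell count with hemoglobin, which has a row), so 28 overstates the number of separate signals.
- The parameters with specific safety measures in Protocol 8.1.4 are largely those with a PCS row.
- The protocol leaves worsening undefined. One could say that a move from normal to high is already worsening, but then the word would add nothing to new.
- SAP 12.3 is absent from the text available for review. The table of contents lists it as ECGs, so it is unlikely to hold a laboratory count.

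**Conclusion.** The point holds as a gap in the laboratory tables, undeclared in SAP Section 8. For 28 of 35 blood parameters, no by-arm laboratory table counts worsening of an abnormality already present at baseline. For a further 4, such worsening is counted only when it takes the value above a fixed ULN multiple.

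This rests on taking worsening to mean something beyond new, and on Table 3 being complete as it stands. How many subjects would be affected cannot be stated, because the documents give no rates of abnormal baselines. The denominator issue is real but small.

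Safety is descriptive in this 104-subject study and the primary result is not touched. The SAP should still be corrected, because following it as written omits an output the protocol commits to.

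**What to change.** In SAP 12.2:

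- Keep the at-risk row for new abnormalities, limited to subjects with at least one post-baseline value.
- For each parameter and direction, add a by-arm count of subjects already out of range at baseline whose worst on-treatment value moves further out in the same direction. The denominator is those abnormal at baseline with a post-baseline value. The SAP's existing safety window of last dose + 5 days can define on-treatment.
- Define worsening by parameter type before unblinding. For enzymes and bilirubin, use a proportional rise or a move to a higher ULN-multiple band. For tightly regulated analytes (sodium, calcium, chloride, red-cell indices), use a margin scaled to the width of the reference range. A uniform 50% rise would not work: with an assumed sodium ULN of 145 mmol/L, a subject starting at that limit would need 1.5 × 145, about 218, so the row would always be zero.
- Report new, worsening, and new or worsening.

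If the sponsor prefers to limit this to selected parameters, these should include at least bilirubin, ALP, electrolytes and coagulation, and the limitation should be stated in SAP Section 8.

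The cost is SAP wording, longer tables and a conventional cut-off for worsening. All the data are already collected.

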4.2 Exclusion Criteria

Subjects who meet any of the following criteria will be excluded from participation in the study:

1. Abnormal liver function test at the Pre-Screening Visit or the Screening Visit (aspartate aminotransferase or alanine aminotransferase $>2 \times$ the upper limit of normal [ULN], total bilirubin $>1.5 \times$ ULN, or alkaline phosphatase $>2 \times$ ULN based on appropriate age and gender normal values). Subjects with bilirubin $>1.5 \times$ ULN and history of Gilbert's syndrome may be included; reflexive direct bilirubin testing will be used to confirm Gilbert's syndrome;
2. Moderate (Grade B) or severe (Grade C) chronic hepatic impairment according to the Child-Pugh classification;

3. Active liver disease (e.g., cirrhosis, alcoholic liver disease, hepatitis B [HBV], hepatitis C [HCV], autoimmune hepatitis, liver failure, liver cancer), history of liver transplant, known diagnosis of human immunodeficiency virus (HIV), or acquired immune deficiency virus;
4. Triglyceride value ≥ 500 mg/dL (5.65 mmol/L) at the Pre-Screening Visit or the Screening Visit;
5. Moderate to severe renal insufficiency defined as an estimated GFR < 60 mL/min/1.73m² (calculated using The Chronic Kidney Disease Epidemiology Collaboration equation) at the Pre-Screening Visit or the Screening Visit;
6. Abnormal urinalysis (proteinuria greater than trace or any male or non-menstruating female with greater than trace hematuria), confirmed by reflexive urine protein:creatinine ratio testing;
7. Uncontrolled thyroid disease: hyperthyroidism or hypothyroidism as defined by thyroid-stimulating hormone (TSH) below the lower limit of normal or $> 1.5 \times$ ULN, respectively, based on results from the Pre-Screening Visit or the Screening Visit. If controlled, treatment should be stable for at least 3 months prior to the Screening Visit;
8. Type 1 diabetes mellitus or uncontrolled type 2 diabetes mellitus (hemoglobin A1c [HbA1c]) value $> 8.5\%$ based on results from the Pre-Screening Visit or the Screening Visit, or taking a thiazolidinedione (ie, pioglitazone or rosiglitazone);
9. New York Heart Association Class III or IV heart failure (see [Appendix C](#));

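### SAP Table 3 counts creatine kinase, urine blood and qualitative urine protein abnormalities without regard to baseline, so the protocol's new-or-worsening counts are only partly delivered

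*SAP*

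**What the plan says.** SAP 12.2, Table 3, has 11 PCS rows. Three are defined relative to baseline: creatinine ("> 0.3 increase from baseline"), estimated GFR and hemoglobin. The other eight are absolute levels:

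- ALT, AST and BUN: >2 × ULN
- CK: >3 × ULN
- Urine blood and qualitative urine protein: present
- Quantitative urine protein and protein/creatinine ratio: >ULN

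The counting period is set by "Summaries will be given for any time post-baseline", and the denominator by "The denominator for a given percentage will be the number of subjects who had a post-baseline assessment for the corresponding parameter". Neither sentence refers to the baseline value. Single-occurrence counts are repeated within each statin-intensity stratum.

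The same section also plans shift tables, and adds that "a summary will be provided of the number of subjects who shifted to high or low during the study". There the rule does depend on baseline: "The denominators will be the number of subjects at risk for shifting". The urinalysis parameters listed for these summaries include protein, albumin and their creatinine ratios. They do not include urine blood or a separate qualitative protein result.

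Protocol 9.3.2, like the Synopsis, says of safety laboratory data: "Frequency counts of new or worsening abnormalities will also be provided". SAP section 8, which records departures from the protocol, mentions none here.

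At entry, Protocol 4.2 has no CK criterion. Exclusion 6 on urine reads: "Abnormal urinalysis (proteinuria greater than trace or any male or non-menstruating female with greater than trace hematuria), confirmed by reflexive urine protein:creatinine ratio testing".

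**The concern.** A safety count at a fixed threshold is read as a count of what happened after dosing. If a subject can enter it with an abnormality that pre-dates the first dose, the two arms share a background of cases that has nothing to do with study drug. A real difference is then harder to see, and an uneven split of baseline cases can mimic or hide one.

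The three rows matter because the protocol and SAP both single out muscle and renal laboratory findings for particular attention. CK >3 × ULN is also the level at which Protocol 8.1.4.3 sends the reader to Appendix E, so a by-arm count of new crossings is the figure a safety reader would look for. No planned table gives it. For urine blood, the PCS table is the only planned by-arm count of any kind.

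**Working it through.** **Step 1. Which rows are exposed.** Set each absolute-level row against the entry criteria and the shift summary.

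| Row | Limit at entry (Protocol 4.2) | New cases counted in the shift summary? |
|---|---|---|
| ALT, AST >2 × ULN | Excluded above the same level at (pre-)screening | Yes, at the normal-range limit |
| BUN >2 × ULN | None direct; eGFR <60 excluded, so unlikely | Yes, at the normal-range limit |
| Quantitative protein, protein/creatinine >ULN | Exclusion 6 | Yes, at the same limit as the PCS row |
| CK >3 × ULN | None | Only at the normal-range limit |
| Urine blood present | Trace, menstruating women and unconfirmed findings not excluded | No |
| Qualitative protein present | Trace and unconfirmed findings not excluded | No |

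The last three rows remain. Take a subject with CK 1.5 × ULN at baseline and 4 × ULN at Week 8. This subject is already high, so is not at risk of shifting to high and is missed by that summary. The PCS table counts the subject, but cannot tell this case from one at 4 × ULN before dosing.

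**Step 2. Arm size.** The plan has 26 per arm in each of two strata: 26 + 26 = 52 per arm, 104 in total. The basis reproduces. A two-sided t-test at 0.05 with difference 17 and SD 20 needs 23 evaluable per arm (power 80.5%), and 23/0.90 = 25.6, rounded up to 26.

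**Step 3. Dilution.** Let b be the proportion meeting the criterion at baseline, p the probability that a baseline case is positive again later, and i the new-onset rate. The planned PCS proportion is

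b[p + (1 − p)i] + (1 − b)i = i + bp(1 − i).

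The between-arm difference is therefore (i_gem − i_plc)(1 − bp).

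The documents give none of b, p or i. Assume p = 1, with i = 10% on gemcabene and 2% on placebo (8 points):

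- b = 10%: 0.10 + 0.90 × 0.10 = 19.0% vs 0.10 + 0.90 × 0.02 = 11.8%; difference 7.2 points
- b = 20%: 28.0% vs 21.6%; difference 6.4 points
- b = 30%: 37.0% vs 31.4%; difference 5.6 points

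At the low end, b = 2% or 5% gives 8 × 0.98 = 7.8 or 8 × 0.95 = 7.6 points. With half persistence (p = 0.5), b = 10%, 20% or 30% gives 7.6, 7.2 or 6.8 points.

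An at-risk count returns 10% vs 2% in every case, on 52(1 − b) subjects per arm: 46.8, 41.6 or 36.4 for b = 10%, 20% or 30%.

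**Step 4. Chance imbalance.** The SD of the between-arm difference in baseline-positive counts is √(2 × 52 × b(1 − b)):

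- b = 10%: √9.36 = 3.1 subjects
- b = 20%: √16.64 = 4.1 subjects
- b = 30%: √21.84 = 4.7 subjects

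For scale, a true 8-point difference is 0.08 × 52 = 4.2 subjects. Within a stratum of 26 per arm, the SD in percentage points is 100√(2b(1 − b)/26) = 8.3, 11.1 or 12.7.

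**The case against.** The strongest reply is that the PCS tables supplement the shift summary and need not do its work. The protocol does not tie its promise to PCS thresholds, and the shift summary already counts new abnormalities with at-risk denominators for ALT, AST, BUN, CK, quantitative protein and protein/creatinine ratio. For the last two, the boundary is the PCS boundary itself. This stands. A reader might infer that the SAP breaks the protocol's promise outright, and the documents do not support that. What is missing is narrower: urine blood, qualitative protein, new crossings of CK 3 × ULN, and worsening within the abnormal range.

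Three other readings are also too strong.

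- That Table 3 ignores baseline throughout. Creatinine, eGFR and hemoglobin are measured against it.
- That earlier abnormalities are reported as drug toxicity. The SAP calls these out-of-range values at any time post-baseline and makes no causal claim.
- That the counts are biased toward one arm. Randomization removes any expected bias.

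It is also fair to say that no safety hypothesis is tested, that all laboratory values of flagged subjects are listed, and that consecutive occurrences are tabulated. With about 52 per arm, a reader could reconstruct baseline status by hand. A listing is not a frequency count, however. Protocol 1.3 reports no proteinuria or hematuria in earlier studies, which lowers the stakes for the urine rows without closing the gap. Finally, exclusion 6 may make 20% or 30% prevalence too high.

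**Conclusion.** The point holds for three rows: CK >3 × ULN, urine blood and qualitative urine protein. For these, the plan has no by-arm count of subjects who newly meet the criterion, and the protocol's undertaking is only partly met. ALT, AST, BUN, quantitative protein and protein/creatinine ratio are largely covered by eligibility or by the shift summary.

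The size depends on assumptions. At 10% to 30% persistent baseline positivity, an 8-point difference loses 0.8 to 2.4 points, and chance imbalance is of the same order as the difference itself. At 2% to 5%, the loss is 0.2 to 0.4 points. For the urine rows, carry-over also depends on whether a trace result is scored as present, which Table 3 does not say, or on menstrual or unconfirmed findings. The consequence is confined to descriptive safety tables and does not touch the efficacy analysis. This is a worthwhile low-cost improvement and no threat to the trial's conclusions.

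**What to change.** In SAP 12.2, for the absolute-level rows of Table 3, and at least for CK, urine blood and qualitative urine protein:

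1. Count subjects who meet the criterion post-baseline and did not meet it at baseline (last pre-dose value, as defined in SAP 9.3).
2. Use as denominator the subjects not meeting it at baseline who have a post-baseline assessment. This is the at-risk rule the section already applies to shifts.
3. Show subjects already meeting the criterion at baseline on a separate line, marking those whose value worsened.

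Leave the creatinine, eGFR and hemoglobin rows unchanged. Applying the rule to ALT, AST, BUN, quantitative protein and protein/creatinine ratio would be consistent but would change little.

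The cost is SAP wording, minor programming and slightly smaller denominators. No new data are needed, since the chemistry panel and urinalysis are taken before dosing on Day 1. One limitation remains: menstrual hematuria is intermittent, so a woman negative at baseline and positive later would still count as new.
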